## 7.10. Treatment after the End of the Study

When the subject is withdrawn from all investigational products, the subject will be treated as determined by the attending physician.

# 7.11. Treatment of Investigational Product Overdose

Subjects with suspected overdose should be monitored until investigational product can no longer be detected systemically (at least 5 half-lives). Follow-up physical examination with laboratory testing should be performed between 10 and 14 days after drug concentrations are undetectable and before the subject is discharged from the investigator's care. Any AEs or SAEs that occur as a result of an overdose should be reported to the GSK Medical Monitor.

# 8. STUDY ASSESSMENTS AND PROCEDURES

The study consists of three periods: screening, treatment and follow-up.

Table 8	Time and Events Table

Procedures	Screen/ Run-in	Treatmer 4 week c			End of Therapy/Early Withdraw	Follow- up	Post Treatment (can be phone contacts)
	Up to 28 days prior 1 st dose	Every cycle (4 weeks) on day 1 (-2/+1)	Every 2 cycles (8 weeks) (-2/+1)	Every 3 cycles (12 weeks) (-2/+1)		28 days after last drug admin.	Every 12 weeks
Written Informed Consent	Х						
Subject Demography	Х						
Medical History	Х						
Disease History	Х						
Therapy History	Х						
Inclusion/Exclusion Criteria	Х						
Evidence of HER-2 or EGFR positive CTCs	X						
HER-2 negative primary tumour 	Х						
Clinical Tumour Assessment	Х			x	x		
CAP CT or MRI scan 	Х			x	x		
Brain CT or MRI scan 	(x)						
Bone scan	Х			(x)	(x)		
Bone X-ray or CT 	(x)			(x)	(x)		
Survival Follow Up							Х
PET substudy 	Х	х					
Safety Assessments	S					•	
Concomitant	Х	Х			х	Х	
Medication							
Physical	Х	х			х	х	Х
Examination							
Vital Signs	Х	Х			Х	Х	х
ECOG PS	Х	Х			х	Х	х
12-lead ECG	Х		Х		Х		
ECHO or MUGA	Х		Х		х		
Toxicity evaluation		Х				Х	Continued

Continued

Procedures	Screen/	Treatment		End of	Follow-	Post	
	Run-in	4 week c	ycles		Therapy/Early	up	Treatment
					Withdraw		(can be
							phone contacts)
	Up to 28 days prior 1 st dose	Every cycle (4 weeks) on day 1 (-2/+1)	Every 2 cycles (8 weeks) (-2/+1)	Every 3 cycles (12 weeks) (-2/+1)		28 days after last drug admin.	Every 12 weeks
Adverse Events 		х					
SAE 		Х					
Hematology	Х	Х			х	Х	
Chemistry	Х	Х			Х	Х	
Pregnancy Test 7	S	As clinically indicated					
Investigational proc	duct						
Dispensing		Х					
Assess compliance		Х			х		

#### Table 8 Time and Events Table (Continued)

1. According to the local lab. It will be centrally re-assessed after patient registration

2. Allowable window for tumour imaging is  $\pm$  7 days

3. To be performed only if CSN or meningeal involvement are suspected

4. To be performed only if bone metastases are clinically indicated

5. PET substudy will be conducted in selected patients in the UK centre only.

6. AE and SAE should be assessed on Day one of every cycle and unscheduled visit.

7. Serum pregnancy test: serum within 14 day from 1st dose of Lapatinib

## 8.1. Critical Screening Assessments

All patients eligible for screening must sign an informed consent for the study before any study-related procedures are performed.

The screening period can least up to 28 days before first study drug administration.

The required observations are:

- Demography: date of birth, race,
- Medical an Therapy history
- Concomitant Medications
- Disease History: details of malignancy date of diagnosis, primary tumour histology, cancer stage, HER -2, EGFR and hormonal receptors status on primary tumours, previous cancer treatment for adjuvant and metastatic setting, ongoing toxicities related to previous treatment,

- Vital Signs: blood pressure, pulse rate, body temperature, body weight and height
- Physical Examination
- ECOG: it is recommended, wherever possible, that a patient's performance status will be assessed by the same person throughout the study.
- 12 lead ECG
- ECHO or MUGA
- Hematology, Chemestry (ANC, PLT, Hb, Total bilirubin, serum creatinine or Calculated Creatinine, ALT (SGPT), AST (SGOT), LDH, alkaline phosphatase)
- For all childbearing potential female a negative serum pregnancy test must be obtained within 14 days before starting Lapatinib treatment
- For the Italian sites (stratum 1) Evaluation of HER-2 status on CTCs: 2 blood samples will be sent to the central laboratory (Prato hospital) for CTC evaluation.
- For the UK sites (stratum 2) Evaluation of EGFR status on CTCs: 2 blood samples will be sent to the central laboratory (Hammersmith hospital) for CTC evaluation

For patients resulting CTC HER-2 + or EGFR+, a Paraffin-embedded tumour block or at least six unstained 4  $\mu$  sections of primary tumour will be collected and sent to the central laboratory. Italian samples should be sent to Prato hospital and UK samples should be sent to Hammersmith hospital.

**NOTE:** All laboratory assessments will be performed locally. Lab normal ranges must be provided to GSK before study start. For the purposes of this study, examinations or laboratory analyses that must have results provided by the day of the scheduled visit and recorded in CRF.

# 8.1.1. Procedures for blood and tumour tissue samples shipment to the central laboratory

All blood and tumour tissue samples must be clearly labelled with the patient number, protocol number, site number, and collection date. Details for the preparation and shipment of samples will be provided before the beginning of the study in a specific procedure manual.

Investigators should select patients whose primary tumour has been locally defined as HER-2 negative (i.e. no gene amplification or IHC 0/1+ or IHC 2+ and no amplification). Central confirmation of the HER-2 negative status will be required after study registration. Accordingly, during screening the investigator should verify that a paraffinembedded tumour block or at least six unstained 4  $\mu$  sections of the primary tumour will be available for shipment at the central lab (Hospital of Prato, Oncology Unit for Italian sites and Hammersmith Hospital for the UK sites).

#### GM2007/00215/03

[figure not shown]
#### CONFIDENTIAL

At the respective central lab, the HER-2 status on the primary tumour will be evaluated by FISH using standard criteria and manufacturer instructions for PathVysion Kit (Abbott Laboratories).

HER-2 and EGFR evaluation on CTC will be performed by the means of the CellSearch equipment (Immunicon, Huntingdon Valley, PA, USA). The CellSearch Circulating Tumour Cell Kit is intended for the enumeration of circulating tumour cells (CTC) of epithelial origin (CD45-, EpCAM+, and cytokeratins 8, 18+, and/or 19+) in whole blood.

The CellSearch HER-2 Tumour Phenotyping Reagent and the CellSearch EGFRTumour Phenotyping Reagent are used for identify those CTCs over-expressing HER-2 and EGFR respectively. For detail on methods refers to Appendix 3.

#### Flow-chart for blood and tumour tissue samples shipment to the central laboratory

Two blood samples (10 + 10 ml) will be shipped to the respective central laboratory for CTC evaluation. If the analysis is positive for presence of HER-2 over-expressing CTCs, *HER2* gene amplification will be evaluated by FISH. The patient will be eligible if the following criteria are met:

- For HER-2 positive CTCs
  - $\geq$  50% CTCs are HER-2 positive and FISH in CTCs is positive or inconclusive
  - < 50% CTCs are HER-2 positive and FISH in CTCs is positive
- For EGFR positive CTCs
  - Presence of EGFR positive CTCs

# 8.2. Clinical Visit Schedules and Assessment during Study treatment and Follow up Periods

The Study Treatment Period is from start of the first dose of lapatinib on Day 1 until discontinuation of study treatment. Refer to the Time and Events Table 8 for the study assessments that need to be performed at each visit during the Study Treatment Period.

Follow up will commence from the time of stopping study drug. It consists of Follow up, 28 days after last dose of lapatinib and Survival follow up every 12 weeks after Follow up (can be assessed by phone contact if the patient cannot attend the visit). Refer to the Time and Events Table 8 for the study assessments that need to be performed.

# 8.3. Efficacy

## 8.3.1. Methods, Scope and Schedules of Disease Assessment

The following methods are acceptable for disease assessments in this study. The disease assessment scope and schedules are to be performed as clinically indicated.

**CT and MRI:** Conventional CT and MRI should be performed with contiguous cuts of 10mm or less in slice thickness. Spiral CT should be performed using a 5mm contiguous reconstruction algorithm; this specification applies to the tumours of the chest, abdomen, and pelvis. Tumours of head and neck, and extremities usually require specific protocols

### NOTE: x-ray, ultra sound, etc. are NOT PERMITTED by the protocol.

**Brain CT or MRI**: are required only if CNS or meningeal involvement are suspected, to rule out brain or meningeal metastasis.

**Bone Scan:** Bone scan must be performed at screening (including evaluation of skull, total spine, clavicle, ribs, pelvis, and long bones). The exam must be repeated every 12 weeks ( $\pm 2$  weeks) until progression if bone metastases have been diagnosed.

If a subject's bone-scan lesions are consistent with tumour metastasis, or are consistent with non-malignant lesions, confirmatory imaging assessments are not necessary. The anatomic sites and nature of the lesions must be documented in the CRF.

If bone scan lesions are equivocal for tumour metastasis, a confirmatory imaging assessment must be performed using X-ray, CT or MRI to determine the nature of the lesion. The lesion sites and nature of lesions must be documented in the CRF. For lesions that are confirmed as tumour metastasis, the same imaging modality must be used for all the subsequent follow-up bone lesion assessment.

Total tumour burden must be assessed within 4 weeks before starting first dose of lapatinib treatment. Follow-up tumour evaluations will be performed at 12 weekly intervals, unless for the disease progression is suspected, to confirm a partial or complete response. Allowable window for tumour imaging studies is  $\pm$  7 days.

If a patient inadvertently misses a prescribed tumour evaluation or a technical error prevents the evaluation, the patient may continue treatment until the next scheduled assessment, unless signs of clinical progression are present.

In cases where there is suspicion of progression before the next scheduled assessment, an unscheduled assessment is to be performed

#### 8.3.1.1. Measurability of Tumour Lesions at Baseline

All measurements should be recorded in metric notation, using a ruler or calipers. All identified tumour lesions are to be classified as measurable or non-measurable per RECIST criteria [Therasse, 2000].

**Measurable lesions:** lesions that can be accurately measured in at least one dimension with the longest diameter  $\ge 20$  mm using conventional techniques, or  $\ge 10$  mm with spiral CT scan.

**Non-measurable lesions:** all other lesions, including lesions too small to be considered measurable (longest diameter < 20 mm using conventional techniques or < 10 mm with spiral CT scan), and the following lesions and disease sites: bone lesions, ascites, pleural/pericardial effusions, lymphangitis cutis/pulmonis, and cystic lesions.

**Measurable disease:** subjects presenting with at least one measurable lesion at baseline are identified as having **measurable disease.** 

#### 8.3.1.2. Determination of Target Lesion

At baseline, all the lesions must also be categorized as "Target" or "non-Target" lesions using the following RECIST guideline.

**Target lesions:** all measurable lesions up to a maximum of five lesions per organ and 10 lesions in total, representative of all involved organs should be identified as *target lesions*, and measured and recorded at baseline.

Target lesions should be selected on the basis of their size (lesions with the longest diameter) and their suitability for accurate repeated measurements (either by imaging techniques or clinically). Lesions that are present within a previously irradiated area cannot be selected as target lesions.

**Non-target lesions:** all other lesions (or sites of disease) should be identified as non-target lesions, and should also be recorded at baseline. Measurements of these lesions are not required, but the presence or absence of each should be noted throughout subsequent assessments.

#### 8.3.1.3. Response Evaluation of Measurable Disease

A sum of the longest diameter (LD) for all target lesions will be calculated and reported as the baseline sum LD. The baseline sum LD will be used as reference by which to characterize the overall tumour response. During Treatment Assessments, any new lesion(s) must be recorded in the CRF. If the lesion(s) noted at baseline is not evaluated at the subsequent Treatment Assessment, this will be noted as 'not done' (ND) in the CRF.

RECIST Response criteria for target and non-target lesion(s) are presented in Table 9.

Evaluation of Target Lesions				
Complete response (CR)	Disappearance of all target lesions			
Partial response (PR)	At least a 30% decrease in the sum of the LD of target lesions, taking as a reference the baseline sum LD			
Progressive disease (PD)	At least a 20% increase in the sum of the LD of target lesions, taking as a reference the smallest sum LD recorded since the treatment started or the appearance of one or more new lesions			
Stable disease (SD)	Neither sufficient shrinkage to qualify for PR nor sufficient increase to qualify for PD, taking as reference the smallest sum LD since the treatment started			
Not evaluable (NE)	Any subject who cannot be classified by one of the four preceding definitions			
Evaluation of non-Target Lesion	S			
Complete response (CR)	The disappearance of all non-target lesions			
Incomplete response/Stable Disease (SD)	The persistence of one or more non-target lesion(s)			
Progressive disease (PD)	The appearance of one or more new lesions and/or unequivocal progression of existing non-target lesions			

Table 9	RECIST Response Criteria for Target and non-Target L	esions
---------	--	--------

New bone scan lesions that are equivocal will be considered as new malignant lesions if a confirmatory assessment using X-ray, CT or MRI is not available, and the subject will be determined as having progressive disease.

If a bone assessment is missing at baseline, any new bone lesions identified after the first dose that is either consistent with or equivocal for tumour metastasis will be considered as new bone (malignant) lesions and the subject will be considered as having progressive disease.

The best overall response is the best response recorded from the start of the treatment until disease progression/recurrence (taking as reference for PD the smallest measurements recorded since the treatment started).

Table 10 shows the overall response for all possible combinations of tumour responses in target and non-target lesions, with or without the appearance of new lesions.

Target Lesions	Non-Target Lesions	New Lesions	Overall Response
CR	CR	No	CR
CR	Incomplete response/SD	No	PR
PR	Non-PD	No	PR
SD	Non-PD	No	SD
PD	Any	Yes or No	PD
Any	PD	Yes or No	PD
Any	Any	Yes	PD

#### Table 10Evaluation of Best Overall Response

Subjects with a global deterioration of health status requiring discontinuation of treatment without objective evidence of disease progression at that time should be classified as having "symptomatic deterioration". Every effort should be made to document the objective progression even after discontinuation of treatment.

In some circumstances it may be difficult to distinguish residual disease from normal tissue. When the evaluation of CR depends on this determination, it is recommended that the residual lesion be investigated (fine needle aspirate/biopsy) to confirm the CR status.

The purpose of this phase II trial is to reject lapatinib from further study in this indication if it was insufficiently active, and to accept it for further study if it was active. "Activity" is defined here as tumour response according to the RECIST criteria

Activity will be assessed from the time of starting the study drug until PD or unacceptable toxicity or death whichever occurs first. This will be performed by tumour assessment as above described.

# 8.4. Safety

## 8.4.1. Physical Examination

Physical examination is assessed at Screening, on Day 1, every Cycle (4 weeks) on day 1 until discontinuation of study treatment. Physical examination includes body weight and evaluation of the subject's medical conditions. Any new or worsening of medical conditions from the screening condition should be recorded in the AE or SAE CRF.

## 8.4.2. Vital Signs

Vital signs, including height, weight, heart rate, temperature and blood pressure should be obtained at Screening, on Day 1, every Cycle (4 weeks) on day 1 until discontinuation of study treatment.

## 8.4.3. ECOG PS

ECOG PS is assessed at Screening, on Day 1, every Cycle (4 weeks) on day 1 until discontinuation of study treatment.

## 8.4.4. Clinical Laboratory Assessment

Hematology, Chemistry (ANC, PLT, Hb, Total bilirubin, serum creatinine or Calculated Creatinine, ALT (SGPT), AST (SGOT), LDH, alkaline phosphatase) should be obtained at Screening, on Day 1, every Cycle (4 weeks) on day 1 until discontinuation of study treatment or as clinically needed.

Bilirubin fractionation is recommended if total bilirubin  $>2 \times ULN$  when testing is available.

See Section 7.3.2 for details on Liver Chemistry Stopping and Follow-up criteria.

## 8.4.5. Criteria for Evaluating Asymptomatic Cardiac events

Cardiac Events will be obtained for at Screening and on Day 1, every 2 Cycles (8 weeks) until discontinuation of study treatment or as clinically needed.

If a subject experiences a  $\geq 20\%$  decrease in LVEF relative to baseline AND the LVEF is below the institution's lower limit of normal (LLN), another evaluation of LVEF must be performed 2 weeks later while still receiving study drug.

Upon completion of the first repeat evaluation of LVEF, the procedures described in Section 7.3.1 must be followed.

## 8.4.6. Toxicity Evaluation

Toxicity Evaluation should be obtained at Screening, on Day 1, every Cycle (4 weeks) on day 1 until discontinuation of study treatment

## 8.4.7. 12 Lead Electrocardiogram and ECHO or MUGA

12-lead ECG will be obtained for at Screening and on Day 1, every 2 Cycles (8 weeks) until discontinuation of study treatment or as clinically needed. Prior to each ECG test, the subject should be at rest for approximately 10 minutes. The subject should be in the semi-recumbent or supine position; the same position must be used for all subsequent ECG tests.

ECHO or MUGA will be obtained for at Screening and on Day 1, every 2 Cycles (8 weeks) until discontinuation of study treatment or as clinically needed. The same method must be used throughout the study.

# 8.5. Positron Emission Tomography (PET) Sub-study

A subgroup of subjects enrolled into stratum 2 (UK study group only) will be asked to participate in a sub-study using PET to quantify the potential early response to lapatinib treatment.

**Response criteria for PET study**: PET will be used to quantify response by calculating the change in PET uptake parameters like SUV (Standardised Uptake Value), Ki (constant for net irreversible uptake of tracer) and FRT (Fractional retention time). This will help in identifying early responders to treatment. PET will help in measuring MAP kinase activity and proliferation, both of which have been shown to be down regulated by lapatinib via its upstream blockade of EGFR and HER-2 receptor tyrosine kinases. Further details are provided in Appendix 4.

# 8.6. Long term remission (related to Amendment 01 – applicable only in UK)

Investigation	Timeframe	Number of procedures
PET scan	Screening then 2 weeks	2
Bone Scintogram	Screening then 3, 6, 12 and 18 months	5
MUGA scan	Screening	1
CAP CT	Screening then 3, 6, 9, 12 and 18 months	6
Bone X-Ray	Screening then 3, 6, 9, 12 and 18 months	6

In the study, there is not a defined stop for the study treatment. In the event of long term remission, even unlikely, the following screening regimen is applied for these subjects:

In the event of long term remission, any imaging performed after 18 months will only be done if clinically indicated (i.e. under standard IR(ME)R practice it is only done if the results will be of benefit to the patient's clinical care).

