**Methods**: This PET substudy is planned to recruit up to 14 patients (using the same sample size calculation as in our previous study with similar tracers) who have diagnosed metastatic breast cancer or metastatic disease which is progressing in spite of treatment. All patients would need to be ER positive. The other receptor status will be as per the main study. Patients should also have received some form of adjuvant endocrine treatment in the past for breast cancer. All patients will undergo a pre-treatment single session PET scan using [C]choline and [F]FLT. Three 10mls venous blood samples would be taken during each PET scan (totalling 30mls per PET scan) to calculate radioactivity counts and metabolite of the [11C] choline radiotracer. They will then be asked to start 1500mg/day of oral lapatinib. At the end of approximately two weeks of treatment, the same PET scan will be repeated to find out if early change in uptake of both tracers is demonstrable, reflecting early activity of lapatinib.

**Statistical considerations**: From reproducibility studies using [18F]FLT in untreated and metastatic breast cancer conducted by the same team the calculated standard deviation (SD) for Ki (constant for net irreversible uptake of [18F]FLT) was 2.0 and 3.61 in untreated and metastatic patients and the mean was 3.6 and 7.3 respectively. Preliminary results for [11C]choline are not available but are expected to be similar.

A sample size of approximately 14 in each group will have 80% power to detect a difference in means of 3.7 (the difference between the metastatic group mean, m1, of 7.3 and the primary group mean, m2, of 3.6) assuming that the metastatic group standard deviation, s1, is 3.61 and the primary group standard deviation, s2, is 2 (ratio of primary group to metastatic group standard deviation is 0.554) using a Wilcoxon (Mann-Whitney) rank-sum test with a 0.05 two-sided significance level. Statistics power calculation done by [name], Imperial College Statistics Service.

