**Results**: Dynamic images of PET will be analysed by drawing ROI (region of interest) around the tumours. A population arterial input function will be applied to the image data to derive various parameters of tracer delivery (K1) and irreversible uptake (Ki). Other parameters of uptake obtained will be SUV (standardised uptake value) and AUC (Area under tracer concentration-time curve). A significant change in uptake parameters from pre to post-treatment would imply inhibition of MAP kinase activity and proliferation due to the effect of lapatinib.

**Primary End Point**: Change in uptake of of [11C]choline and [18F]FLT from pre to post treatment with lapatinib.

The ability to image MAP kinase modulation using PET would serve as a marker of the pharmacological early effect of lapatinib.

Secondary End Point: None.

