#### Radiation dosimetry:

For [11C]choline-effective dose=1.036mSv per scan [Kobori, 1999]

For[18F]FLT -effective dose=7.326mSv per scan [Vesselle, 2003]

Therefore the total effective dose per patient for two PET scans is 16.724mSv. The radiation dose is not significant as all patients will be exposed to radiation from Xrays, CT scans and bone scans which form part of routine investigations.

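### Table 8 puts the on-treatment PET scan on day 1 of every 4-week cycle, against one repeat at about 2 weeks in Appendix 4 and Section 8.6; and UK Section 8.6 sets a sparser imaging regimen without saying when, or whether, it displaces Sections 8.3.1 and 8.4.7

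*Protocol*

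**What the plan says.** **PET.** The PET row of Table 8 is marked at screening and in the column headed "Every cycle (4 weeks) on day 1 (-2/+1". Its footnote 5 reads "PET substudy will be conducted in selected patients in the UK centre only"; it limits the centre and gives neither timing nor number of scans. Appendix 4 describes one pre-treatment session and one repeat: "At the end of approximately two weeks of treatment, the same PET scan will be repeated". The PET line of Section 8.6 reads "Screening then 2 weeks", with two procedures. The dosimetry paragraph of Appendix 4 concludes: "Therefore the total effective dose per patient for two PET scans is 16.724mSv". The sub-study's primary endpoint is the change in tracer uptake "from pre to post treatment with lapatinib", and on size, "This PET substudy is planned to recruit up to 14 patients".

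**Section 8.6.** This section is headed as applying to the UK only. It states: "In the event of long term remission, even unlikely, the following screening regimen is applied for these subjects". The table that follows lists PET, bone scintigram, MUGA, CT and bone X-ray from screening to month 18. MUGA appears at screening only, and CT at screening and months 3, 6, 9, 12 and 18. After month 18, imaging is left to clinical indication. Section 8.3.1 asks for tumour evaluation every 12 weeks. Section 8.4.7 asks for ECHO or MUGA every 8 weeks until treatment stops, by one method throughout. Section 5.1 sets no fixed end to treatment; it can run until progression.

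**The concern.** Table 8 is the schedule that site staff work from. No column in it offers a week-2 visit, so a site that followed the PET row would miss the post-treatment scan on which the sub-study endpoint rests. It would also give more radiation than the stated total for two scans.

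Section 8.6 raises a different problem. Its schedule begins at screening, when nobody can yet be known to be in long-term remission. The body of the section does not define that state. It is sparser than 8.3.1 and 8.4.7 and mentions neither, so a UK site cannot tell whether it replaces or supplements them. At stake are the dating of late progression in the few stratum 2 patients still on treatment (time to progression, duration of response and of clinical benefit) and clarity that cardiac monitoring continues while lapatinib is given.

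**Working it through.** **1. The stated PET dose.** Appendix 4 gives 1.036 mSv for [11C]choline and 7.326 mSv for [18F]FLT.

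- One session: 1.036 + 7.326 = 8.362 mSv.
- Two sessions: 2 × 8.362 = 16.724 mSv.

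This reproduces the stated figure exactly, so the dosimetry assumes two sessions.

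**2. Table 8 read literally, through the week-12 visit.** Day 1 of cycles 2, 3 and 4 falls at weeks 4, 8 and 12.

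- Screening plus cycles 2, 3 and 4: 4 sessions, 4 × 8.362 = 33.448 mSv, which is 2.0 times the stated dose.
- Also counting day 1 of cycle 1: 5 sessions, 5 × 8.362 = 41.810 mSv, which is 2.5 times the stated dose.

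**3. Distance of the week-2 scan from the Table 8 windows.** Table 8 gives no unit for −2/+1; days are assumed. Two weeks of treatment is taken as day 15.

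- The cycle 1 window closes on day 1 + 1 = 2, and 15 − 2 = 13 days.
- The cycle 2 window opens on day 29 − 2 = 27, and 27 − 15 = 12 days.

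The scan is therefore 12 to 13 days outside either window. If the unit were weeks, the cycle 2 window would open on day 29 − 14 = 15, so the scan would sit exactly on its edge; a window that wide is implausible for a 4-week cycle.

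**4. Is the PET mark really in the every-cycle column?** The ECG and ECHO/MUGA rows of the same table leave that column empty and are marked in the 8-week column, which agrees with Section 8.4.7. The column positions therefore look reliable.

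**5. Section 8.6 against the main schedule, to month 18.** Month 18 is taken as week 78 (assumption). Counts include screening; a separate day-1 cardiac test is not counted.

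| Procedure | Main text | Section 8.6 |
|---|---|---|
| Tumour imaging | 12-weekly (8.3.1): 1 + 6 = 7 | CT: 6, none at month 15 |
| ECHO or MUGA | 8-weekly (8.4.7): 1 + 9 = 10 | MUGA: 1, at screening |
| Bone scan, if bone metastases | 12-weekly (8.3.1): 1 + 6 = 7 | 5, none at months 9 or 15 |

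The procedure counts printed in 8.6 agree with its own time points.

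**6. Start point.** The amended text of 8.6 recorded under Amendment 01 in Appendix 6 describes long-term remission as no progression after 18 months of therapy. That description is not in the body of 8.6. Even with it, a table running from screening to month 18 cannot be applied prospectively to patients identified only after month 18. Only the sentence on imaging after month 18 could then operate.

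**The case against.** **The PET error is clerical.** Sections 5.1 and 8.5 send the reader to Appendix 4, and all scans are done at one imaging site under separate consent. This stands as a limit on the harm. It does not remove the conflict, because Table 8 is the operative visit schedule and its footnote does not point to Appendix 4.

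**Section 8.6 may be only a tally of radiation exposures.** It has a column counting procedures, lists only imaging with ionising radiation, omits ECHO, ECG and laboratory tests, and closes on UK radiation practice. This largely stands. A reader might infer that 8.6 withdraws cardiac monitoring. The documents do not support that: nothing in 8.6 cancels 8.4.7, and ECHO is not mentioned. The text nevertheless calls the table a regimen that is applied, and a MUGA at screening followed by ECHO would break the one-method rule of 8.4.7. One clarifying sentence is warranted.

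**The CT difference need not be a conflict.** Table 8 allows CT or MRI, so 12-weekly evaluation up to month 18 could be kept with MRI. Suspected progression still triggers an unscheduled assessment under 8.3.1. Both points stand. How much imaging to do between months 12 and 18 is a radiation trade-off for the sponsor.

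**A reader might also infer that 8.6 does not say whom it covers.** It does: UK subjects in long-term remission. What its body lacks is the definition and the point of application.

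**Conclusion.** The point holds as a minor one: the text is wrong as written. Table 8 conflicts with Appendix 4 and Section 8.6 on the timing of the repeat PET scan, and with the dosimetry on the number of scans. The dosimetry should not be read as fixing the 2-week timing; that comes only from Appendix 4 and 8.6. The literal excess is 4 to 5 sessions against 2 through week 12 (33.4 to 41.8 against 16.724 mSv), in at most 14 patients. The range depends on whether day 1 of cycle 1 is counted; the distance from the windows assumes −2/+1 is in days.

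Section 8.6 lacks a definition in its body, a workable start point and a rule of precedence over 8.3.1 and 8.4.7. A reader might infer a threat to the primary endpoint or a material safety gap. Neither is supported. Response rate and clinical benefit rate are essentially unaffected, because the missing CT falls after month 12. Cardiac checks would lapse only if 8.6 were read as replacing 8.4.7. The documents do not say how many patients would reach long-term remission, so no event count is offered.

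**What to change.** - **Table 8:** remove the every-cycle PET mark and add to footnote 5 that PET is done at screening and about week 2 only, with a reference to Appendix 4.
- **Section 8.6, definition:** put the 18-month description of long-term remission from the Amendment 01 text into the body of the section.
- **Section 8.6, precedence:** state that 8.3.1 and 8.4.7 apply up to the point where 8.6 takes over, and name that point. If the reduced CT schedule is meant to start before month 18, say from when.
- **Section 8.6, cardiac monitoring:** state that ECHO or MUGA every 8 weeks, by one method, continues for as long as the patient takes lapatinib.

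The cost is one table mark, one footnote and two or three sentences. No patients, analyses or scans are added, since 8.4.7 already requires the cardiac tests. Any CT or MRI between months 12 and 18 remains the sponsor's choice and is not part of this correction.
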